6.1 Diet

2-8 weeks prior to the first study visit, all patients will be counseled by an NIH dietician (in person or via long-distance contact) to follow a moderate diet composed of ~50% kcal from carbohydrates (focusing on complex carbohydrates and avoidance of concentrated sugars like juice and candy) and 30% or less kcal from fat (focusing on decreasing intake of trans and saturated fats and increasing intake of mono-unsaturated fats), with an emphasis on mixed meals (combination of protein, carbohydrate and fat). Patients should maintain their customary physical activity level throughout the study. Patients will be advised to limit alcohol consumption to moderate use (not more than 3 drinks/week and not more than 1 drink/day for females and not more than 5 drinks/week and not more than 2 drinks/day for males). One drink = 5 ounces (150 mL) of wine or 12 ounces (360 mL) of beer or 1.5 ounces (45 mL) of hard liquor.

6.2 Medications

6.2.1 Pre-study Medications

With the exception of insulin and sulfonylureas subjects will continue their pre-admission medications at stable doses throughout the study. This includes oral hypoglycemic agents, and other medications either related or unrelated to lipodystrophy or its complications. Insulin and sulfonylurea doses may be reduced per investigator judgment in case of hypoglycemia.

6.2.2 ISIS 304801

6.2.2.1 Formulation, storage conditions/stability:

Study Drug (ISIS 304801 or placebo) characteristics are listed below.

The Study Drug is contained in glass prefilled syringes (PFS). The Study Drug must be stored securely at 2° to 8° Celsius and be protected from light. The investigative team will provide patients with instructions in Study Drug storage and administration.

Study Drug Characteristics

Study Drug	ISIS 304801	Placebo
Strength	200 mg/ mL	Not Applicable
Volume/Formulation	1.5 mL solution per PFS	1.5 mL solution per PFS

Dose	300 mg once weekly	Not applicable
Route of Administration	SC	SC

6.2.2.2 Availability

ISIS 304801 and placebo are supplied by Ionis Pharmaceuticals.

6.2.2.3 Initial Drug Shipment and Re-Supply

A completed Drug Request Form must be emailed, at least 5 days prior to the expected delivery date, to Ionis Clinical Supplies.

6.2.2.4 Study Drug Accountability

The study staff is required to document the receipt, dispensing, and return/destruction of Study Drug supplies provided by the Sponsor. At the end of the study, and after full accountability is performed on study drug or site closure, study drug destruction will occur at NIH.

6.2.2.5 Study Drug Administration

For each individual patient, Study Drug will be administered SC as a single 1.5 mL injection once weekly for Weeks 1-68. Self-administration will be allowed after appropriate training of the patient and/or caregiver. Patients should receive 1 dose per week, with weeks always defined relative to Study Day 1. For example, if a patient receives the first dose on a Monday, subsequent doses should be given on Mondays, if possible. If a patient misses an injection, or if dosing on the usual day is not possible, the patient can reschedule the injection provided that 2 doses are administered at least 2 days apart.

Every effort should be made to ensure the previous week's dose is given 7 days prior to a scheduled clinic visit. Subjects will not be removed from the study because of missed dosing; however, subjects missing more than 2 doses before Week 13 may not be evaluable for the primary endpoint.

6.3 Study Procedures

6.3.1 Study Schedule

A detailed schedule of study visits and testing to be performed at each visit is given in Appendix A.

6.3.2 Prescreening

Prior to the first study visit, patients will undergo prescreening via an in-person NIH visit under another protocol, or via long-distance review of medical history and records, to maximize the likelihood that subjects will meet all inclusion/exclusion criteria at the time of the initial study visit. Dietary counseling will be provided in-person or via long-distance communication 2-8 weeks prior the initial study visit as per section 6.1, and prior to the written informed consent process. If an outside LDL-C lab result is available and is within 3 months of a subject's initial NIH visit, the outside value will be considered as part of their enrollment criteria. The test will be remeasured once at NIH but will ensure there are no delays in study procedures as a result of this test not being available until ~7 days after it is drawn.

6.3.3 Initial Visit – Includes Screening (Week -1) and the first week of dosing (Week 1)

Subjects will be admitted to the Metabolic Research Unit in the NIH Clinical Center. Upon admission, they will undergo a history and physical examination, and baseline labs will be obtained. Height, weight, blood pressure, resting pulse, and temperature will be obtained. Subjects will undergo the informed consent process prior to any study-related testing.

Testing used to assess subject eligibility includes:

- Physical examination (including skin-fold measurements, blood pressure)
- Urinalysis and/or 24 hour urine for protein and blood
- Lipid panel
- Fasting insulin
- Pregnancy test (females)
- Cardiac troponin T
- Hemoglobin A1c
- Hepatic panel
- Serum creatinine
- Thyroid function tests
- Coagulation panel (PT, aPTT)
- Viral hepatitis studies
- 12-Lead EKG
- Echocardiogram

If a subject meets all eligibility criteria, he/she will undergo randomization and will proceed with the Week 1 schedule per Appendix A.

6.3.4 In-person follow-up visits

Patients will come to NIH for follow-up visits every 4 months. Testing will be performed as per the Study Schedule (Appendix A)

6.3.5 Home nurse visits

Home nurse visits for safety and/or efficacy labs and vital signs will be conducted every week (unless the patient is coming for an in-person visit) for the duration of the study, as detailed in Appendix A. Home (or visits at a location convenient for the subject) visits will be completed by trained service providers, sourced through a home health care agency, GlobalCare Clinical Trials. Service providers will receive detailed training on all necessary study procedures and are also required to comply with patient privacy and data protection laws as well as regulatory guidelines for Good Clinical Practices and ICH guidelines. Home health care is provided to ease patient burden while still allowing for adequate safety monitoring. If feasible, patients can also complete these visits as outpatient visits at the NIH clinical center. Visits will be approximately 1 hour in length. In the unlikely event a service provider is unavailable to collect blood from a subject, the NIH study team will send a prescription to the subject so that they can have their labs drawn by a local lab facility. Prior approval to cover the cost of the lab tests is required by NIH. Patients will be made aware there is a

possibility they may need to cover the costs through either their health insurance provider or pay out of pocket.

All visits (home and in-person) will have a visit window of at least +/- 7 days. All reasonable attempts should be made to ensure compliance with the visit schedule as outlined in Appendix A. However, in the event that a visit does not occur or is delayed, all subsequent visits should be calculated based on the time elapsed since Day 1 rather than from the date of the previous visit.

6.3.6 Telephone follow-up

Telephone contact between the study team and each subject for review of adverse events, concomitant medications, and general study requirements will be conducted every month for the placebo controlled period and the first 6 months of the open label extension, and every 2 months thereafter (unless the patient is coming for an in-person visit), as detailed in Appendix A.

6.3.7 Post-Treatment

After completion of the open label extension (week 68), patients will enter the 12-week post-treatment evaluation period. This period consists of home platelet monitoring every week for six weeks and then again at a single NIH visit on week 80 as outlined in Appendix A.

Immediately after week 68, or after the post-treatment evaluation period, patients may choose to receive an additional 12 months of open label drug (up to 24 months, total). They will be offered this option if their triglycerides improved by $\geq 50\%$. Justification for this additional extension are:

- a. The patients received $\geq 50\%$ improvement in triglycerides and they have no other effective treatment options.
- b. To collect additional safety data over a longer term
- c. To collect additional efficacy data over a longer term

Home health care visits will not be available during the extended open-label period. Patients must obtain platelet and other safety monitoring locally through their health insurance provider or pay out of pocket. This monitoring will include weekly CBC for platelet count, and monthly CBC with differential, lipid panel, coagulation studies, urine protein:creatinine ratio, liver function tests, and chemistry panel. Hemoglobin A1c will be measured every 3 months. Study staff will remain in weekly contact with patients to review safety labs and any adverse events. Patients will return to NIH at the end of the 12 month extended open-label use period, or earlier if there are any safety concerns that, in the judgment of the PI, require in-person evaluation. During the NIH visit at the end of the 12 month period, patients may undergo optional evaluation including any test listed in section 6.4 except liver biopsy. All concomitant medications, including those for diabetes or hyperlipidemia, may be adjusted as clinically appropriate per the judgment of the investigator during the extended open-label period.

6.3.8 Follow-up Visits for Early Termination from Treatment Period

Any patient who discontinues early from the placebo-controlled or OLE periods will be encouraged to attend a final in-person follow-up visit (Week 80 visit assessments per Appendix A) approximately 12 weeks after their last dose of Study Drug. If the patient declines or is unable to participate in the above, a home nurse

visit for safety/efficacy labs (equivalent to week 74 visit in Appendix A) and telephone follow-up will be attempted, ideally ~12 weeks from the last dose of Study Drug.

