5.2 Statistical Methods for Data Analysis

Descriptive statistics such as mean and standard deviation (or median and interquartile range) will be used to summarize data in raw scale or change from baseline per visit.

The primary outcome, change in log₁₀ TG at Week 16 from baseline, and continuous secondary outcomes will be compared between ISIS 304801 and placebo groups using either two-sample t-test or Wilcoxon rank sum test as appropriate based on change from Baseline at Week 16. Changes from baseline based on tertiary/exploratory outcomes as well as change on log₁₀ TG at Week 16 will be examined using either one-sample t-test or Wilcoxon signed rank test as appropriate.

Repeated measures analysis of covariance using linear mixed models will be conducted in order to investigate trends on selected response variables and to compare active and placebo group while possible covariates are taken into account. There are three possible covariates: (1) Baseline level of the outcome of interest, (2) Baseline level of ApoCIII, and (3) Change in ApoCIII before and after the 16 week active drug intervention.

Inclusion of covariates will be checked using linear mixed models by checking Akaike Information Criteria (AIC) with inclusion of one covariate at a time

Analyses will include all available data even if patients do not adhere to their assigned treatments. Additional analyses will examine the effect of adherence to study results. We will also investigate the effect of missing data on the results using standard methods for missing data.

A p-value of 0.05 or less is considered significant.

6. Experimental Plan

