7.5 Safety Monitoring Rules

In addition to the standard monitoring of clinical safety parameters, the following guidelines are provided for the monitoring of selected parameters chosen based on preclinical and clinical observations. For the purposes of safety monitoring baseline is defined as the average of Day 1 pre-dose assessment and the last measurement prior to Day 1.

Confirmation Guidance: At any time during the Study (Treatment or Post-Treatment Periods), the initial clinical laboratory results meeting the safety monitoring criteria presented below **must be confirmed** by performing measurements (ideally in the same laboratory that performed the initial measurement) on new specimens. All new specimen collections should take place as soon as possible (ideally within 3 days of the initial collection). For stopping rules, if the initial laboratory result is observed during the Treatment Period, the results from the retest **must be available** prior to administering the next dose of Study Drug (ISIS 304801 or placebo).

Re-dosing Guidance: Patients with initial laboratory test values that reach a stopping rule must not be re-dosed until the re-test results are available. In general, patients who do not meet the stopping rules based upon retest may continue dosing. However, the Investigator will decide whether additional close monitoring of the patient is appropriate. If any of the stopping criteria described below are met below and are confirmed, the patient will be permanently discontinued from further treatment with Study Drug (ISIS 304801 or placebo), evaluated fully as outlined below and will be entered into the post-treatment evaluation portion of the study. Consultation will be conducted between the Investigator and the Ionis Medical Advisor as needed.

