100K/mm ³ - 140K/mm ³	Weekly 300 mg study drug administration	Monitor every 1 week unless otherwise specified Obtain additional lab tests if 2 occurrences of platelet count 100 K/mm ³ -- 140K/mm ³ or 1 occurrence of platelet count ≤ 100K/mm ³ **
75K/mm ³ - 100K/ mm ³	Permanently reduce dose frequency to 300 mg every 2 weeks	Monitor every 1week unless otherwise specified Obtain additional lab tests if 1 occurrence of platelet count ≤ 100K/mm ³ **
50K/mm ³ - 75K/mm ³	If occurs while on dose of 300 mg every 2 weeks or 150 mg every week then permanently discontinue Study Drug, otherwise dose pause. When platelet count returns to >100K/mm ³ restart dosing at dose frequency of 300 mg every 2 weeks or 150 mg weekly ₁ (in consultation with the Ionis Medical Advisor as needed).	Monitor every 2-3 days until two successive values are > 75K/mm ³ then monitor every 1 week Consider discontinuation of antiplatelet/agents/NSAIDS/anticoagulant medication Obtain additional lab tests if 1 occurrence of platelet count ≤ 100K/mm ³ **
≤ 50 K/mm ³	Permanently discontinue Study Drug	Monitor daily until 2 successive values show improvement, then monitor every 2-3 days until 2 successive values are > 75K/ mm ³ . Patient should be evaluated by a hematologist to provide diagnostic and therapeutic management Steroids recommended*. It is strongly recommended that, unless the patient has a medical contraindication to receiving glucocorticoids, the patient receives glucocorticoid therapy to reverse the platelet decline. Monitor triglyceride levels weekly and continue AE monitoring during steroid therapy. Discontinue antiplatelet agents/NSAIDS/anticoagulant medication while platelet count <50K/mm ³ if

		possible Obtain additional lab tests if 1 occurrence of platelet count $\leq 100\text{K}/\text{mm}^3$ **
--	--	---

*Recovery in platelet count may be accelerated by administration of high dose steroids. Treatment guidelines for immune thrombocytopenia (Provan et al. 2010) recommend Dexamethasone 40 mg daily for 4 days every 2-4 weeks for 1-4 cycles; Prednis(ol)one 0.5-2 mg/kg/d for 2-4 weeks then taper; or Methylprednisolone 30 mg/kg/day for 7 days (**note:** may require continuation with oral steroids after methyl prednisolone)

**See Appendix J

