7.8 Withdrawal Criteria

1. **Withdrawal of consent.** A subject wishes to withdraw from the study as stated in the informed consent (all subjects reserve the right to withdraw from the study without prejudice).
2. **Adverse event (or SAE).** The patient develops laboratory test abnormalities that meet any of the stopping rules listed above, or any other adverse event that in the investigator's opinion necessitates withdrawal from the study.
3. **Investigator judgment.** An investigator feels it is in the subject's best interest to terminate participation. The detailed reasoning behind this decision will be documented.
4. **Pregnancy.**
5. **Ineligibility.** Includes study entry criteria violation.
6. **Significant Protocol Deviation.** Includes subject noncompliance or start of an unacceptable concomitant medication.

The reason for discontinuation of study treatment must be recorded in the electronic case report form (eCRF) and source documentation. All efforts will be made to complete and report the observations as thoroughly as possible up to the date of withdrawal. All information, including the reason for withdrawal from study, must be recorded in the eCRF.

Any patient who withdraws consent to participate in the study will be removed from further treatment and study observation immediately upon the date of request. These patients should be encouraged to complete the early termination study procedures and observations at the time of withdrawal. For patients withdrawn for reasons other than withdrawal of consent, every effort should be made to complete the early termination study procedures and observations at the time of withdrawal.

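### No readable rule secures a triglyceride at the original Week 16 date for patients who permanently stop drug in the blinded phase, although the primary test is at Week 16

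*Combined protocol and SAP*

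**What the plan says.** Section 5.2 compares the arms on change in log10 TG from baseline to Week 16, by two-sample t-test or Wilcoxon rank sum test. It adds: "Analyses will include all available data even if patients do not adhere to their assigned treatments".

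For patients who stop treatment early, these provisions set the follow-up:

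- **Section 6.3.8**, which expressly covers the placebo-controlled period, encourages "a final in-person follow-up visit (Week 80 visit assessments per Appendix A) approximately 12 weeks after their last dose of Study Drug". For those who do not attend, a home draw equivalent to the Week 74 visit is attempted on the same 12-week clock. Section 7.5.8 largely repeats this.
- **Section 7.5** says that a patient with a confirmed stopping rule "will be entered into the post-treatment evaluation portion of the study". Section 6.3.7 describes that portion: "This period consists of home platelet monitoring every week for six weeks", followed by one NIH visit.
- **Section 7.8**, for withdrawals other than withdrawal of consent: "every effort should be made to complete the early termination study procedures and observations at the time of withdrawal".

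Three further provisions bear on the point:

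- **Section 6.3.5**: "Home nurse visits for safety and/or efficacy labs and vital signs will be conducted every week", for as long as the study lasts; the glossary counts a patient as on study until the last visit. On timing: "All visits (home and in-person) will have a visit window of at least +/- 7 days".
- **Section 7.6.3, platelet table**, for counts at or below 50K: "Monitor triglyceride levels weekly and continue AE monitoring during steroid therapy".
- **Section 5.1** sets the enrolment goal as 10 patients who complete 16 weeks of active drug. Its allowance above 10 is for screen failures.

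Two wordings elsewhere do not fit Section 5.2. Section 6.2.2.5 says that patients who miss more than two doses before Week 13 might not be evaluable for the primary endpoint. Section 7.7 gives Week 12 as the primary analysis time point.

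**The concern.** An analysis that keeps patients regardless of adherence needs a Week 16 value from those who stopped. The readable follow-up rules for permanent stoppers are timed from the last dose or from withdrawal, and none is tied to Week 16. A patient whose last dose is in Week 8 has the 12-week visit at Week 20; a last dose in Week 12 puts it at Week 24.

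Permanent stops for platelets, liver tests or other adverse events can be caused by the drug, so the missing values need not be balanced between arms. The Week 16 comparison would then move toward patients who stayed on drug. With five patients per arm, one patient is 20% of an arm. The mixed model and missing-data analyses in Section 5.2 can use earlier values, but they cannot replace a Week 16 value that was never drawn.

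Patients whose dosing is only paused or reduced keep their Week 16 visit and are not affected.

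**Working it through.** **The plan's own figure.** Section 5.1 gives 5 per arm, difference 0.50, SD 0.25 and two-sided 0.05. The noncentral t distribution with 8 degrees of freedom and noncentrality 0.50/(0.25 × √(2/5)) = 3.16 gives power 79.1%. This reproduces the stated 79%.

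**When a stopper would happen to be seen near Week 16.** Let L be the week of the last dose, L = 1 to 14, and let w be the window in weeks. Section 6.3.5 sets the window at 7 days or more, so w = 1 gives a floor. Placing the withdrawal assessment one week after the last dose is an assumption, as is a Week 74-type draw 6 weeks after it (Week 74 is 6 weeks after Week 68).

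| Assessment | Condition | w = 1 | w = 2 |
|---|---|---|---|
| 12-week visit | abs(L + 12 − 16) ≤ w | L = 3–5 | L = 2–6 |
| Withdrawal assessment | abs(L + 1 − 16) ≤ w | L = 14 | L = 13–14 |
| Both combined | | 4 of 14 | 7 of 14 |
| 6-week draw, if it includes TG | abs(L + 6 − 16) ≤ w | L = 9–11 | L = 8–12 |
| All three combined | | 7 of 14 | 12 of 14 |

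These are counts of stop weeks, not probabilities.

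**Weekly home visits.** If they continue until the 12-week visit, a stopper who accepts that visit is still being seen at Week 16 when L + 12 ≥ 16, that is L ≥ 4. Whether those draws include TG depends on the Appendix A laboratory rows, which could not be read.

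**Steroid monitoring.** Suppose an untapered course of d weeks starts at L + 1. It reaches Week 15, the early edge of a 7-day window, when L + 1 + d ≥ 15. For d = 2 that means last doses from Week 12 on; for d = 4, from Week 10 on. A taper or repeat cycles would extend this.

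**Bias in an assumed case.** The documents give no stop rate. Take one of five active patients stopping and keeping a share k of the effect at Week 16. The Section 5.1 planning data give a net effect of −0.485 − (−0.011) = −0.474 log10.

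- Stopper left out: −0.474, a reduction of 100 × (1 − 10^−0.474) = 66.4%.
- Everyone included: −0.474 × (0.8 + 0.2k).
- Standard error at 4 v 5: 0.25 × √(1/4 + 1/5) = 0.168.

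| k | Net, everyone | Overstatement if left out | Gap, log10 | Gap / SE | Reduction, everyone |
|---|---|---|---|---|---|
| 0 | −0.379 | 25.0% | 0.095 | 0.57 | 58.2% |
| 0.25 | −0.403 | 17.6% | 0.071 | 0.42 | 60.5% |
| 0.50 | −0.427 | 11.1% | 0.047 | 0.28 | 62.6% |
| 0.75 | −0.450 | 5.3% | 0.024 | 0.14 | 64.5% |

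**Power, at the planned 0.50 and SD 0.25.** Noncentral t gives 79% at 5 v 5 and 73% at 4 v 5. Simulated t-tests (400,000 trials) with the stopper included give 46, 57, 67 and 74% for k = 0, 0.25, 0.50 and 0.75.

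**The case against.** The strongest objection is that this is a claim of absence, made while part of the schedule cannot be read. The Appendix A laboratory rows could put TG in the weekly home draws. Section 6.3.5 describes those draws as possibly including efficacy labs and counts visits from Day 1 when an earlier one is missed or late. Section 6.4.5 schedules LDL monitoring every 4 weeks, and Appendix B lists TG in the same lipid panel. Section 6.3.9 requires follow-up after an adverse-event withdrawal. Section 6.3.8 describes its fallback draw as covering efficacy labs, which makes a TG there likely and favours the higher counts of 7 and 12 of 14.

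Part of this stands. The unreadable rows limit confidence, and the week counts do not measure how often Week 16 would be missing. But the 4-weekly labs are set by time on treatment, the adverse-event follow-up names no TG, and the Day 1 rule concerns missed or delayed visits. A general laboratory schedule would not by itself override the specific rules for stoppers in Sections 6.3.8 and 7.5.

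Two objections on size also stand. Section 2.3.4 describes a long duration of response, which points to the small end of the bias for stops near Week 16. Adding an off-drug value also has a price: power falls below the 73% of the left-out analysis in three of the four assumed cases. The argument for the draw is therefore bias, not power.

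**Conclusion.** The concern holds and should be fixed, with medium confidence because of the unreadable laboratory rows. Followed as written, the readable rules can leave a patient who stops because of the drug without a value for the stated primary test. In the assumed case of one active stopper in five, omission overstates the net effect by 5 to 25%, or 0.14 to 0.57 of a standard error. Both the single stopper and the share of effect kept (0 to 75%) are assumptions.

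The two wording mismatches are minor. Section 5.2 largely governs over the missed-dose remark in Section 6.2.2.5. The Week 12 reference in Section 7.7 merits correction in its own right, because that rule discourages dose changes only up to the wrong primary time point.

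**What to change.** **Main change, Section 6.3.8.** Require a fasting TG at the original Week 16 date, by home nurse or local laboratory, from every randomised patient who stops drug before Week 16 and has not withdrawn consent. State that it is additional to the 12-week follow-up and that the value enters the primary analysis.

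**Minor corrections.**
- Section 6.2.2.5: confine the missed-dose rule to a named per-protocol sensitivity analysis with a Week 16 cut-off.
- Section 7.7: replace Week 12 with Week 16.

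**Cost.** Protocol wording, and at most one blood draw per early stopper through a route that Section 6.3.5 already provides. If the Appendix A laboratory rows already give a TG at Week 16 after a stop, no extra draw is needed and only the wording changes. The possible loss of power from including diluted responses should be accepted openly.

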Appendix A: Schedule of Study Procedures

Study Period	Pre-Screen	Screen	Double-Blind					Open Label Extension										Post Treatment		
Study Week (from enrollment)	-8 to -2	-1	1	4	8	12	13	16	20	24	28	32	36	40	48	56	64	68	74	80
Study week (from start of open label extension)									4	8	12	16	20	24	32	40	48	52		
Inpatient Visits		x						x				x						x		x
Home Nurse visit**				x	x	x	x		x	x	x		x	x	x	x	x		x	
Telephone contact				x	x	x	x		x	x	x		x	x	x	x	x		x	
Inclusion/Exclusion Criteria	x	x																		
Medical History Review	x	x																		
Vital Signs/Weight/Height		x						x				x						x		x
Physical Exam		x						x				x						x		x
Waist Circumference		x						x				x						x		x
Skinfold measurements		x																		
DEXA Scan			x					x				x						x		
Glucose and Lipid Turnover			x					x				x						x		x
Euglycemic Hyperinsulinemic Clamp			x					x				x						x		x
Mixed Meal Test			x					x				x						x		x
Urinalysis & protein:creatinine ratio		x		x	x		x	x	x	x	x	x		x		x		x		x
Liver Biopsy			x															x		
MRI/MRS liver/heart			x					x				x						x		
Carotid intima-media thickness			x					x				x						x		
12-Lead EKG		x						x				x ¹						x		

7-point plasma glucose			X					X				X						X		X	
Weekly Study Drug SQ Injection			X	X	X	X	X	X	X	X	X	X	X	X	X	X	X	X	X		
Glucometer Dispensation/Training			X																		
Hunger Diary			X					X				X						X		X	
Widespread Pain Diary			X					X				X						X		X	
Quality of Life Assessments			X					X				X						X		X	
Review SMPG and Insulin Dose			X	X	X	X	X	X	X	X	X	X	X	X	X	X	X	X	X	X	X
Diet/Alcohol Counseling	---X---		X	X	X	X	X	X	X	X	X	X	X	X	X	X	X	X	X	X	X
Adverse Events			X	X	X	X	X	X	X	X	X	X	X	X	X	X	X	X	X	X	X
Concomitant Medication Review	X		X	X	X	X	X	X	X	X	X	X	X	X	X	X	X	X	X	X	X

¹ Patients previously treated with placebo, only

² One sample obtained on each of two consecutive days

³ Sampling schedule can be found in Appendix C.
 Unless specified, otherwise, PK and Antibodies will be collected predose.
 PK and immunogenicity testing does not need to be collected fasting.

* Platelets will be assessed every week

** Home Health Nurse Visits (or lab draw by local lab facility when needed) will take place every week unless patient will be at NIH for in-person visit.

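### No Week 16 triglyceride assessment is scheduled for a patient who permanently stops blinded drug, although the primary analysis is change at Week 16 regardless of adherence

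*Combined protocol and SAP*

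**What the plan says.** On the primary analysis, Section 5.2 states: "The primary outcome, change in log₁₀ TG at Week 16 from baseline, and continuous secondary outcomes will be compared between ISIS 304801 and placebo groups". The test it names is a t-test for two samples or its rank-sum counterpart, applied to that change. On the patients included it states: "Analyses will include all available data even if patients do not adhere to their assigned treatments". On missing values it says only: "We will also investigate the effect of missing data on the results using standard methods for missing data".

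Three places govern what happens after a patient permanently stops blinded drug:

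- Section 6.3.8 covers any early discontinuation from the placebo-controlled period. It asks for a final in-person visit, specified as "Week 80 visit assessments per Appendix A) approximately 12 weeks after their last dose of Study Drug". If the patient cannot or will not attend, the fallback takes place at the patient's home: "visit for safety/efficacy labs (equivalent to week 74 visit in Appendix A) and telephone follow-up will be attempted, ideally ~12 weeks from the last dose". Section 7.5.8 repeats the visit text.
- Section 7.8 covers patients who are withdrawn but have not themselves revoked consent: "every effort should be made to complete the early termination study procedures and observations at the time of withdrawal". It lists meeting a stopping rule among the withdrawal criteria, so one patient can fall under both 6.3.8 and 7.8.
- The re-dosing guidance in Section 7.5 sends confirmed stopping-rule cases to the post-treatment portion. Section 6.3.7 describes this as weekly home platelet checks for six weeks and then one NIH visit.

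In Appendix A, the row "MRI/MRS liver/heart" is marked at Weeks 1, 16, 32 and 68 but not at Week 80, and the same is true of DEXA. Appendix E agrees: its post-treatment column counts no DEXA and no MRI. The readable part of Appendix A has no early-termination column.

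**The concern.** An analysis of everyone at Week 16 regardless of adherence needs a Week 16 measurement on those who stop. The follow-up schedule is built around time since last dose, or time of withdrawal, and not time since Day 1. A patient who follows it exactly can therefore reach the analysis with no Week 16 triglyceride value, or with one taken at another time and in another treatment state. Section 5.2 does not say which value, if any, would then stand for Week 16.

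With 5 patients per arm, one such patient is a fifth of an arm. Section 5.1 attributes the ten extra places under the accrual ceiling to screen failures and makes no allowance for loss after randomisation. Liver volume and hepatic steatosis, listed as secondary outcomes in Section 4.2.2, are also affected: a stopper followed under 6.3.8 has no scheduled MRI/MRS after baseline.

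The protocol protects the endpoint elsewhere. Section 7.5.8 brings the primary-endpoint assessments forward, where possible, before glycemic rescue starts. Permanent stoppers have no comparable provision.

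**Working it through.** **Plan's own figure.** Section 5.1 gives 5 per arm, difference 0.50, SD 0.25 log10 mg/dL, two-sided alpha 0.05 and 79% power. For a two-sample t-test, noncentrality = d / (SD × √(1/n1 + 1/n2)) = 0.50 / (0.25 × √(2/5)) = 3.162 with 8 degrees of freedom. Power is 79.05%, so the stated figure reproduces.

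**Visit timing under 6.3.8.** Visit week = last-dose week + 12. Section 6.3.5 allows a window of at least ± 7 days, so Week 16 is taken as Weeks 15 to 17.

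| Last dose (week) | 6.3.8 visit (week) | In Week 16 ± 1? |
|---|---|---|
| 1–2 | 13–14 | No |
| 3–5 | 15–17 | Yes, by coincidence, about 12 weeks off drug |
| 6–15 | 18–27 | No |

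Only 3 of the 15 possible last-dose weeks reach the window. A visit under 7.8 takes place at withdrawal. Its value is early and largely on-drug, so it is mistimed in the other direction.

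**If the value is missing.** The formula is the same, with unequal groups:

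- One active value missing (4 v 5): 0.50 / (0.25 × √(1/4 + 1/5)) = 2.981, 7 degrees of freedom, power 72.5%.
- Two active values missing (3 v 5): 0.50 / (0.25 × √(1/3 + 1/5)) = 2.739, 6 degrees of freedom, power 63.0%.

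**If an off-drug value is used as Week 16.** Let a fraction r of the 0.50 effect remain at that visit. With one stopper among 5 active patients, the mean difference is (4 × 0.50 + r × 0.50) / 5 = 0.40 + 0.10r. With two it is 0.30 + 0.20r. Power is from simulation (400,000 trials per case, t-test):

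| Effect retained | One stopper: difference, power | Two stoppers: difference, power |
|---|---|---|
| 0% | 0.400, 46% | 0.30, 22% |
| 25% | 0.425, 57% | 0.35, 38% |
| 50% | 0.450, 67% | 0.40, 55% |
| 75% | 0.475, 74% | 0.45, 69% |
| 100% | 0.500, 79% | 0.50, 79% |

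The number of stoppers and the retained fraction are both assumptions, since the documents give neither.

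**The case against.** The strongest reply is that Section 6.3.5 counts visits from Day 1 and that 6.3.8 does not expressly cancel the Week 16 visit. For some stoppers the text is silent and does not forbid it. But 6.3.5 deals with a visit that was missed or delayed. Section 6.3.8 is the specific rule for stopping and calls its visit final, and 7.5 moves stopping-rule cases to post-treatment follow-up. Silence is not a schedule.

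Four stronger readings are tempting, and the documents do not support them.

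- *Stoppers are never seen at Week 16.* Last doses in Weeks 3 to 5 bring the 6.3.8 visit into the window.
- *The only value obtained is a washed-out one.* No triglyceride offset is given. Section 2.3.4 attributes late glycemic effects to a long duration of response, and a 7.8 visit gives a largely on-drug value. The 46% figure is the extreme of a range.
- *The all-available-data analysis becomes impossible.* Section 5.2 also plans mixed models and missing-data analyses that could use earlier triglycerides. Section 6.3.5 has home visits collecting safety and/or efficacy labs. What remains is that the mixed model is not the stated primary test and the missing-data method is not named.
- *The loss falls on the active arm.* Section 2.3.4 links a mild platelet decrease to active drug and names injection-site reactions as its most frequent adverse events, so imbalance is plausible. But no discontinuation rate is given, and Section 7.6.3 answers several platelet ranges with a pause or dose change.

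Three limits also stand. The point covers permanent stops only: missed doses (6.2.2.5) do not remove a patient, and rescued patients (7.5.8) continue treatment. The 4 v 5 and 3 v 5 figures assume that no further patients are enrolled, while the plan aims for 10 completers within a ceiling of 20. The laboratory rows of Appendix A cannot be read in the extracted text, so triglyceride sampling at other visits cannot be checked.

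**Conclusion.** The point holds for patients who permanently stop blinded drug. Their Week 16 triglyceride assessment is not scheduled, 6.3.8 and 7.8 give different timings, and neither is tied to Week 16. Under 6.3.8 they also have no scheduled post-baseline hepatic steatosis value. This undercuts the Section 5.2 rule of analysing change at Week 16 regardless of adherence, and it is more than missing detail, because following the schedule as written loses or mistimes the primary value.

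The power figures show how sensitive a comparison of 5 per arm is to a single patient. They are not expected losses. They rest on the Section 5.1 inputs and on assumed numbers of stoppers, all on active drug. More enrolment could restore numbers, but it would not supply the Week 16 values of those who stopped.

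**What to change.** - In Section 6.3.8, state that any randomised patient who permanently stops blinded drug keeps the Week 16 assessment, counted from Day 1, unless consent is withdrawn. The minimum is a fasting triglyceride sample by the home-nurse or local-lab route already in Section 6.3.5. Add the planned Week 16 MRI/MRS and clamp if the patient will attend.
- Keep the contact about 12 weeks after the last dose as separate follow-up, and state that it is not used as the Week 16 value.
- Reconcile the timing in Sections 6.3.8 and 7.8.
- In Section 5.2, state that the Day-1-anchored Week 16 value enters the primary comparison, and say how a missing one is handled.

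The cost is a short amendment and, for the few early stoppers, one blood draw or a visit already planned. The change affects data collection only and leaves treatment and safety rules as they are.
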